7.2 Reporting Procedures

Serious Adverse Events (SAEs): SAEs will be reported to NIA and the Data and Safety Monitoring Board (DSMB) members by the PIs or their designees by email within 24 hours of learning of deaths, and 48 hours of learning of non-deaths. Official reports will be

submitted within five business days. The DSMB will request additional information as needed and will determine whether changes to the study protocol are warranted.

Adverse Events (AEs): AEs will be reported to NIA and the DSMB in aggregate form prior to the biannual DSMB meetings.

7.3 Follow-up for Adverse Events

Unresolved AEs will be followed until resolved or considered stable. The health coaches will follow up during subsequent contact until the AE is resolved for participants in the intervention. For those in the HE group, the study nurse will follow-up via phone or EHR until the AE is resolved. For occurring SAEs, the MDs will triage for appropriate medical care within the KP system. The study nurse will follow-up with the participant and through medical records until the condition is stable or resolved.

7.4 Safety Monitoring

This study will be monitored by a DSMB, which will act in an advisory capacity to the NIA and the Principal Investigators, [name] and [name], to monitor participant safety, data quality, and the progress of the study.

8 INTERVENTION DISCONTINUATION

Subjects may withdraw voluntarily from participation in the study at any time and for any reason. Participants will continue to be followed, with their permission, even if the study intervention is discontinued. Follow-up measurement visits will continue to be scheduled if the participant is agreeable. If not, we'll follow-up via phone calls and/or medical record review, as allowed by the participant.

9 STATISTICAL CONSIDERATIONS

9.1 General Design Issues

The primary outcome will be a global cognitive function composite score. To calculate the composite score, each raw test score will be standardized based on the mean/standard deviation from all participants at baseline. Then, the resulting z-scores will be averaged across tests. Secondary outcomes will include change in Alzheimer's risk factors, components of the cognitive composite score, and measures of physical performance, functional ability, and quality of life. Changes made to the protocol due to Covid-19, i.e., switching to telephone data collection, may limit our ability to examine cognitive change effectively, as several of the most important cognitive tests cannot be administered via telephone. Additionally, the onset of Covid-19 may affect the ability of participants to achieve risk factor reduction. In an exploratory outcome we will examine the effect of the Covid-19 pandemic on risk factors. Our hypotheses include the following:

1. We hypothesize that composite cognitive function scores among participants randomized to the SMARRT intervention arm will show better scores, relative to those in the HE control arm. We also hypothesize that the component scores will be improved by the intervention.

2. We hypothesize that participants in the SMARRT intervention will show improvements on Alzheimer's risk factors during the intervention, relative to those in the HE control arm.
3. We hypothesize that additional outcomes including components of the global cognitive function composite, physical performance, functional ability, and quality of life will be improved by the intervention. We also hypothesize that incidence of MCI and Alzheimer's will be lower among participants in the SMARRT arm.

9.2 Sample Size and Randomization

Because this is a pilot trial, our goal is to estimate effect sizes for a larger trial. Therefore, sample size estimates are based primarily on considerations of precision rather than power and effect size. For our primary outcome, our sample size of 200 will enable us to estimate the effect size with a precision of +/- 0.08 SDs, assuming loss to follow-up of 10%, and ICC of 0.6, based on data from the FINGER trial (4). This estimate will be used in combination with a consensus clinically meaningful effect, based on the literature and investigator expertise. For secondary outcomes, we estimate that precision will range from +/- 0.06 SDs to +/- 0.08 SDs, depending on the ICC. We anticipate that conversion to MCI/AD in this two-year trial will be low (<10%); therefore, this outcome is considered exploratory.

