9.4 Data Analyses

We will first assess balance on baseline characteristics of the SMARRT and HE groups using graphical and tabular checks for overlap, and statistical comparisons using t-tests, Wilcoxon, chi-square, and Fisher's exact tests as appropriate. All analyses will use intent-to-treat principles.

Aim 1. To estimate the effect of SMARRT compared to HE on our outcome, repeated measures of the composite cognitive function score obtained at 6, 12, and 24 months, we will use a linear mixed model (LMM), with fixed effects for the baseline score, time, treatment, and the time-by-treatment interaction, as well as random intercepts and slopes. Exploratory analyses will be performed within the intervention group to determine whether there is evidence that the magnitude of the effect varies based on the number or types of risk factors targeted, the extent to which goals are achieved, or the number or type of interventionist contacts. These analyses will be restricted to the intervention group because among controls, the number and type of risk factors targeted will not be assessed, achievement of goals will be undefined, and the number and type of contacts will differ systematically by design. Hence these results will be descriptive and will not estimate effect modification, mediation or dose-response, respectively. We also will use multiple imputation to explore the impact of missing data.

Aim 2. Similar methods will be used to assess the effect of the intervention on continuous Alzheimer's risk factors over two years. Because this is a pilot study, we chose not to pre-specify the benchmarks for change/improvement for each risk factor. Instead, we will quantify the amount of change achieved for each risk factor. Generalized linear mixed models (GLMMs), also with fixed effects for the baseline value, time, treatment, and the time-by-treatment interaction, and random intercepts and slopes, will be used as appropriate to assess treatment effects on binary, count, ordinal, and multinomial risk factors, including the number of risk factors.

Aim 3. LMMs and GLMMs also will be used to compare the impact of SMARRT vs. HE on individual components of the global cognitive score, physical performance, functional ability, quality of life. Finally, Cox proportional hazards models will be used to analyze intervention effects on time to MCI and Alzheimer's.

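### The +/- 0.08 SD precision in section 9.2 is unlabelled and is not a 95% margin for the planned arm difference; the plan's inputs give about +/- 0.23 SD at 24 months or +/- 0.18 SD averaged over visits

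*Combined protocol and SAP*

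**What the plan says.** Section 9.2 states that "sample size estimates are based primarily on considerations of precision rather than power and effect size". For the primary outcome it says that "our sample size of 200 will enable us to estimate the effect size with a precision of +/- 0.08 SDs". The inputs named for that figure are given in these words: "assuming loss to follow-up of 10%, and ICC of 0.6, based on data from the FINGER trial". For secondary outcomes, "we estimate that precision will range from +/- 0.06 SDs to +/- 0.08 SDs, depending on the ICC". It gives no confidence level, formula, contrast or visits, and does not say which SD is the unit.

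The analysis is in section 9.4: a linear mixed model for "repeated measures of the composite cognitive function score obtained at 6, 12, and 24 months", with "fixed effects for the baseline score, time, treatment, and the time-by-treatment interaction" and random intercepts and slopes. Section 9.1 builds the composite by standardising each test at baseline, after which "the resulting z-scores will be averaged across tests"; the text does not re-standardise that average. Section 5.3 defines the primary outcome as two-year change on the composite.

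**The concern.** A reader will normally take a +/- figure in a precision-based sample size paragraph as a 95% confidence margin. With about 90 people per arm and a correlation of 0.6, a margin of 0.08 SD on a difference between arms looks far too narrow.

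This figure carries the whole justification for 200 participants, since no power calculation stands beside it. The pilot exists to estimate effect sizes for a larger trial. Read as a 95% margin, 0.08 promises an interval 0.16 SD wide. If the design yields an interval two to three times as wide, the pilot will say much less about the effect than readers of the plan are led to expect.

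**Working it through.** **Inputs from the documents.** 100 randomised per arm and 10% loss, so n = 90 per arm; ICC 0.6 (section 9.2); baseline score as covariate and outcomes at 6, 12 and 24 months (section 9.4).

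**Assumptions, because the documents are silent.** Two-sided 95% level (z = 1.96); composite SD = 1; the ICC read as one correlation ρ = 0.6 between all visits, baseline included. The trial from which the ICC was taken cannot be checked here.

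**The plan's own figure.** No formula is given. With the stated inputs and the section 9.4 contrasts:

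- 24 months: SE = √[2(1 − ρ²)/n] = √[2(0.64)/90] = 0.119. Half-width = 1.96 × 0.119 = **0.234**. With linear time the SE is 0.117 and the half-width 0.228.
- Mean of three visits: variance factor (1 + 2ρ)/3 − ρ² = 0.733 − 0.360 = 0.373. SE = √[2(0.373)/90] = 0.091. Half-width = **0.179**.

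Ratios to 0.08: 0.234/0.08 = 2.9 and 0.179/0.08 = 2.2. The interval widths are 0.47 and 0.36 SD, against 0.16. As a half-width, 0.08 would give coverage of about 50% at 24 months and 62% averaged.

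**Other 95% contrasts at 90 per arm.** Post-score only at one visit 0.292; change score at one visit 0.261; change averaged over three visits 0.213; adjusted average with a fourth visit 0.170. Adding visits cannot reach 0.08: the adjusted average has a floor of 1.96 × √[2(ρ − ρ²)/90] = 1.96 × √[2(0.24)/90] = 0.143.

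**Readings that come closer to 0.08.**

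| Reading | Result | What it requires |
|---|---|---|
| SE, averaged, gradual loss (assumed retention 97.5/95/90%) | 0.088 | 0.08 to be an SE |
| The same with month 18 (97.5/95/92.5/90%) | 0.084 | Month 18, which section 9.4 omits and section 5.1 makes an optional phone subset |
| SE at 24 months, single-test z-units | 0.074–0.082 | 0.08 to be an SE, and an assumed inter-test correlation r of 0.3–0.4 |
| 95% half-width of yearly slope, baseline as an outcome | 0.125 per year | A slope model with baseline as an outcome |
| The same in single-test units | 0.078–0.086 per year | That model and that unit together |
| 95% half-width, residual variance only, five visits: 1.96 × √[2(0.4)/(5 × 90)] | 0.083 | Between-person variance dropped and baseline counted as outcome data |

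Single-test units arise because the mean of 8 z-scores has SD √[(1 + 7r)/8], which is 0.622 at r = 0.3 and 0.689 at r = 0.4. On that scale the 95% half-widths are 0.146–0.161 at 24 months and 0.111–0.123 averaged.

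The slope readings do not match the plan. With baseline as covariate, as in section 9.4, the yearly slope half-width is 0.171 (0.106–0.118 in single-test units). Over the two years of the primary outcome, the baseline-as-outcome slope gives 0.250 (0.156–0.172).

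**Sensitivity.** Random slopes with an assumed SD of 0.1 to 0.3 per year widen the half-width to 0.241–0.292 at 24 months and 0.182–0.206 averaged. With baseline correlation 0.6 and follow-up correlations of 0.5 to 0.8, the averaged half-width is 0.162–0.208.

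**For scale only.** A 95% half-width of 0.08 needs 2(0.64)(1.96/0.08)² ≈ 769 completers per arm at 24 months, or 2(0.373)(1.96/0.08)² ≈ 449 averaged.

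**Secondary outcomes.** Averaged over three visits, 0.08 and 0.06 as 95% half-widths need ICCs of about 0.94 and 0.97. As SEs they need about 0.73 and 0.86.

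**The case against.** The strongest reply is that this is a missing label and not an arithmetic error. Section 9.2 never mentions 95% or a confidence interval; I supplied the level, the unit, the contrast and the correlation structure. Section 9.1 leaves the composite as an average of z-scores, and on that scale the 24-month SE is 0.074–0.082 with no change to the visits or the baseline adjustment. The excess on that scale is about 1.4 to 2.0 times (0.111/0.08 to 0.161/0.08), not 2.2 to 2.9. Section 9.4 also has random slopes, which the headline values omit. Finally, the figure enters no analysis, and planners of the larger trial will have the pilot's observed interval.

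Much of this stands. How 0.08 was obtained cannot be known, the size of the excess depends on the unit, and the headline values rest on assumptions. The reply does not rescue the printed figure. Random slopes only widen the margin. On neither scale does a 95% half-width for the two-year or averaged difference fall to 0.08 at the inter-test correlations considered. If 0.08 is an SE, its 95% margin is 1.96 × 0.08 = 0.157, and the +/- notation hides that. The figure enters no analysis, but it is still the stated basis for the sample size.

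**Conclusion.** The point holds, and the paragraph is wrong as it stands. The precision is unlabelled. As printed, it is not a 95% margin for the planned two-year or averaged arm difference in composite SDs. On the plan's inputs that margin is about 0.23 SD at 24 months and 0.18 SD averaged, given a 95% level, 90 per arm, a composite SD of 1 and a common correlation of 0.6. Confidence in this bounded claim is high. Whether 0.08 is a mislabelled standard error or rests on another unit or contrast remains open, and only the sponsor can settle it.

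**What to change.** Restate the paragraph in section 9.2 with the confidence level, contrast, visits and SD unit. For example:

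> Pre-Covid planning value: with 90 per arm, a correlation of 0.6 between all visits and no between-person variation in slope, the 95% CI half-width for the between-arm difference is about +/- 0.23 SD at 24 months (about +/- 0.18 SD averaged over 6, 12 and 24 months), in baseline SDs of the composite. Variation in slopes would widen these margins. Precision after March 2020 will differ because some tests could not be given by telephone.

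If 0.08 is a standard error, is in other units, or is per year, label it so and print the 95% half-width beside it. Treat the 0.06 to 0.08 range for continuous secondary outcomes in the same way and state the ICCs assumed. Section 9.4 also plans "to assess treatment effects on binary, count, ordinal, and multinomial risk factors"; an SD margin should not be applied to those outcomes.

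The cost is one paragraph and a short recalculation. The sample size and the analysis stay as they are. The only downside is a less favourable stated precision.

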Study participants will be randomized after the baseline visit in a 1:1 ratio to treatment and control, using procedures described below in Section 9.2.1. The study intervention will begin within eight weeks of randomization. If an appointment with the interventionist has not been scheduled within eight weeks of randomization, a case review will take place between the clinical support team and the intervention team to decide the best way to continue with the participant.

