- Objectively measured physical activity (Actigraphy): participants will wear an ActiGraph wGT3X+ (Pensacola, FL) waist-worn accelerometer for 7 days prior to measurement visits at baseline, 12 months, and 24 months. Data from the ActiGraph will be aggregated using ActiLife software with counts over 1040 per minute used as the threshold for moderate or higher intensity activity (a cut point that appears to be valid for older adults).
- Leisure / Social Activity (PROMIS Satisfaction with Participation in Discretionary Social Activities): 12-item questionnaire which asks individuals to rate how satisfied they have been with their engagement with social and other leisure activities and social connectedness in the past 7 days on a 5-point Likert scale (not at all ... very much).
- Cognitive activity (Cognitive Activity Questionnaire): 11-item questionnaire which asks how often an individual engages in activities such as reading the newspaper, playing games (e.g., crosswords, puzzles), playing a musical instrument, and other cognitively stimulating hobbies/leisure activities on a 6-point Likert scale (once a month/never ... every day).
- Control of cardiovascular risk factors (hypertension, diabetes): Blood pressure and HbA1c values will be ascertained from the KPWA EHR. In addition, at each measurement visit, height, weight, and blood pressure will be assessed. Height and weight will be used to calculate body mass index (BMI).
- Smoking: Participants will be asked to self-report current tobacco usage, including questionnaire items: "Have you smoked even a puff in the last 7 days?" and if yes, "How many cigarettes have you smoked in the last 7 days?"
- Diet (MIND diet score): The Mediterranean-DASH Intervention for Neurodegenerative Delay (MIND) diet combines elements of the Mediterranean and the Dietary Approach to Systolic Hypertension (DASH) diets. The 15-item questionnaire assesses frequency of consumption of specific food types (e.g., green leafy vegetables, red meat) over the past 6 months.
- Depressive symptoms (Center for Epidemiologic Studies – Depression Scale, CES-D): 20-item questionnaire that assess both positive and negative affect over the last week rated on a scale from 0 (rarely or none of the time) to 4 (most or all of the time).

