- Sleep quality (Pittsburgh Sleep Quality Index, PSQI): 19 item questionnaire that assesses sleep quality and disturbances over the past month (not at all, less than once a week, once or twice a week, three or more times a week).
- Potentially harmful medications (identified from KPWA pharmacy database): based on a detailed list of contraindicated medications developed for the intervention (see Intervention section). Additionally, a medication questionnaire will assess the use of over-the-counter [OTC] medications containing ingredients that increase risk of cognitive impairment/dementia.
- The onset of Covid-19 may affect the ability of participants to achieve risk factor reduction. In an exploratory outcome we will examine the effect of the Covid-19 pandemic on risk factors.

b) Individual cognitive domain scores

c) Physical performance (Short Physical Performance Battery, SPPB): The SPPB was developed by the National Institute on Aging (NIA) to provide an objective tool for measuring physical performance in older adults. Each component is individually scored on a scale of 1-4 (balance, lower extremity strength/chair stands, and gait speed/time to walk 4 meters) according to SPPB scoring protocols. The total SPPB score is the sum of the 3 component scores and ranges from 0 to 12. We will also examine scores on subscales (time to complete 5 chair stands, time to walk 4 meters). [Because this requires in-person observation, we have very few timepoints with this data due to Covid-19.]

d) Functional ability (Cognitive Function Instrument, CFI): 14-item self-report inventory of cognitive and functional difficulties in everyday tasks (e.g., remembering appointments, managing finances, driving). Total scores range from 0 to 14, with higher scores indicating greater difficulty in everyday tasks.

e) Quality of life (PROMIS Global Health): 10-item self-report inventory which asks individuals to rate their quality of life including in terms of their overall physical and emotional health.

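### The precision range for secondary outcomes in Section 9.2 makes no allowance for Covid-19 data loss: it is not delivered for SPPB, and is unsupported for the affected cognitive tests and for HbA1c

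*Combined protocol and SAP*

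**What the plan says.** Section 9.2 sizes the pilot on precision: "sample size estimates are based primarily on considerations of precision rather than power and effect size". On the primary composite score it claims: "our sample size of 200 will enable us to estimate the effect size with a precision of +/- 0.08 SDs". That figure takes 10% attrition and an ICC of 0.6, drawn from FINGER, as its inputs. For the rest, "For secondary outcomes, we estimate that precision will range from +/- 0.06 SDs to +/- 0.08 SDs, depending on the ICC". The paragraph gives no range of ICCs, no confidence level and no formula, and it states no separate attrition for secondary outcomes. It then sets conversion to MCI/AD apart as exploratory.

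Other sections describe what data exist:

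- **SPPB** (Section 5.3, item c): "Because this requires in-person observation, we have very few timepoints with this data due to Covid-19". Section 5.1 had scheduled physical function tests at baseline, 6, 12 and 24 months. Section 9.4 (Aim 3) still plans mixed models for physical performance.
- **Cognitive components** (Section 5.2.5, footnote to the visit list): several tests in the battery could not be given by telephone and were not collected after March 2020.
- **HbA1c** (Section 5.3, item a): "Blood pressure and HbA1c values will be ascertained from the KPWA EHR". The same bullet lists height, weight and blood pressure as measured at visits. The Section 5.1 schedule has no blood test.
- **Actigraphy** (Sections 5.1 and 5.3): baseline, 12 and 24 months, so two follow-ups.

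**The concern.** One range is offered for secondary outcomes with very different amounts of follow-up, and the ICC is the only quantity said to move it. Precision also depends on how many participants contribute and on how many follow-up values each has. The protocol itself reports that follow-up is badly depleted for SPPB and cut short for some cognitive tests, yet Section 9.2 carries no adjustment.

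The pilot exists to estimate effect sizes for a larger trial, and precision is its stated justification for 200 participants. Someone using Section 9.2 as the guide would treat an SPPB estimate as being as well determined as one from a questionnaire that can be completed by phone or mail.

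**Working it through.** **Inputs.** 200 randomised (Section 9.2), 1:1 (Section 5.2.4: "randomized after the baseline visit in a 1:1 ratio to treatment and control"), 10% loss, hence 180 evaluable or 90 per arm. ICC 0.6 for the primary outcome. Three follow-ups (Section 9.4: "repeated measures of the composite cognitive function score obtained at 6, 12, and 24 months"). Assumed, because not stated: a 95% two-sided half-width, total SD of 1, compound symmetry, no random-slope variance, and ICC 0.8 for the favourable end (0.06).

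**Step 1: the plan's own figure.** For a baseline-adjusted mean of k follow-ups,

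v(k) = (1 + (k − 1)·ICC)/k − ICC², half-width = 1.96·√(2v/n per arm).

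At ICC 0.6 and k = 3, v = 2.2/3 − 0.36 = 0.373, and the half-width is 1.96·√(2 × 0.373/90) = 0.179. The printed 0.08 is not reproduced. At ICC 0.8 the same formula gives 0.139. Reaching 0.08 at ICC 0.6 would need about (1.96/0.08)² × 2 × 0.3733 = 448 per arm. A reading that uses only within-person variance over five occasions comes close, at 1.96·√(2 × 0.4/5/90) = 0.083, but the protocol does not state it. The steps below take the printed range as correct with full data and ask only how far it would widen.

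**Step 2: fewer follow-ups, all 180 present.**

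- ICC 0.6: v(1) = 1 − 0.36 = 0.64. The ratio is √(0.64/0.373) = 1.309, so 0.08 becomes 0.105.
- ICC 0.8: v(3) = 2.6/3 − 0.64 = 0.227 and v(1) = 0.36. The ratio is √(0.36/0.227) = 1.260, so 0.06 becomes 0.076.
- Actigraphy, two follow-ups, ICC 0.6: v(2) = 1.6/2 − 0.36 = 0.44. The ratio is √(0.44/0.373) = 1.086, about 9% wider.

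**Step 3: one follow-up and half the participants.** Multiply by √2.

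| Data available | ICC 0.6 | ICC 0.8 (assumed) |
|---|---|---|
| 3 follow-ups, 180 people (as printed) | 0.08 | 0.06 |
| 1 follow-up, 180 people | 0.105 | 0.076 |
| 1 follow-up, 90 people | 0.148 | 0.107 |

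The one-follow-up case at ICC 0.8 stays within 0.08 only if the share contributing is at least (0.0756/0.08)² = 0.893, about 161 of 180. On the standard formula itself, at ICC 0.6, the same three rows are 0.179, 0.234 and 0.331.

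**Step 4: fewer participants, same number of values each (the HbA1c question).** The half-width scales as 1/√(share). With 80% contributing, 0.06–0.08 becomes 0.067–0.089; with 50%, 0.085–0.113. The favourable end passes 0.08 when the share falls below (0.06/0.08)² = 0.5625, about 101 of 180. The documents do not say on which side of this HbA1c lies.

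**The case against.** The range is a planning estimate, and the protocol is open about the data loss: Sections 1.1, 3, 5.3 and 9.1 all carry Covid-19 caveats. The mixed models in Section 9.4 will return standard errors that reflect the data in hand, so sparse SPPB data would show up as wide intervals. Section 1.1 ties sizing of the larger trial to the primary objective, and no section names SPPB or HbA1c as a sizing input. All of this stands and limits the consequence. It does not make the printed range right for SPPB.

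Three stronger readings are tempting and are not supported:

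- **The range cannot hold for HbA1c.** A reader might infer this because diabetes is one of eight alternative eligibility factors and testing would follow routine care. That inference is reasonable, but no section gives the share with values. Section 5.2.1 says all potential participants have EHR risk data including laboratory values, though it does not promise an HbA1c or repeats for everyone. Sections 5.2.5 and 8 allow follow-up through records, so EHR outcomes need not suffer visit dropout.
- **SPPB half-widths grow with the square root of the drop in participants.** Section 5.3 reports few timepoints, not few people. Visits lost within a person do not follow that rule, which is why Step 2 is kept separate from Step 3.
- **Every secondary outcome is misstated.** MCI/AD incidence is already set apart, and for actigraphy the missing visit adds only about 9%.

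**Conclusion.** The concern holds in this form. The range in Section 9.2 conflicts with the protocol's own account of SPPB follow-up. It could survive for SPPB only with a high ICC and a nearly complete single follow-up (about 161 of 180 at an assumed ICC of 0.8), which does not fit the wording in Section 5.3. For the cognitive tests not collected after March 2020, the range has no stated basis. For HbA1c it is unsupported and may be too narrow; the documents do not settle which.

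The size is illustrative because no outcome-specific counts are given: up to about 0.105 with one follow-up and full numbers, and about 0.107 to 0.148 if half the participants contribute. These figures rest on compound symmetry, no slope variance, an assumed ICC of 0.8 at the favourable end, and acceptance of a printed range that the standard formula does not reproduce (0.179 against 0.08 for the primary inputs). The fault is a planning figure that does not reflect a data loss disclosed elsewhere; nothing is concealed.

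**What to change.** In Section 9.2, withdraw the single range for secondary outcomes and restate precision by outcome:

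- Give the formula, confidence level and ICC for each figure.
- Use blinded counts, pooled over arms, of participants with a usable baseline and follow-up value, and the visits available. This is needed for SPPB and its timed subscales, HbA1c and the affected cognitive components. Compute actigraphy with two follow-ups.
- Do not keep 0.06–0.08 SD as a benchmark or cut-off for any outcome, questionnaires included, unless it is first re-derived.
- State that outcomes with sparse follow-up, SPPB in particular, are descriptive and will not serve as effect-size inputs for the larger trial.

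The cost is a change of wording and a short recalculation. No new data or participants are needed. The downside is a less favourable stated precision.
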